## **8.14. Treatment After the End of Study**

After the end of the study, each subject will be treated according to standard clinical practice.

# **9. STUDY PROCEDURES**

Subjects will provide written informed consent before any study-related procedures are initiated, including the cessation of prohibited concomitant therapy.

For the timing of assessments and procedures throughout the study, refer to the Schedule of Assessments. Throughout the study, every reasonable effort should be made by study personnel to follow the timing of assessments and procedures in the schedule of assessments for each subject. If a subject misses a study visit for any reason, the visit should be rescheduled within the visit window specified below.

## **9.1. Study Periods, Visits, and Procedures**

### **9.1.1. Visit 1: Enrollment (Day 1)**

Subjects entering from Study AXS-05-TRD-201

Day 1 of this study maybe combined with the End of Study (EOS) Visit in Study AXS-05-TRD-201. Subjects will be instructed not to take study drug (from Study AXS-05-TRD-201) on the morning of Visit 1. Any assessments that are required for both studies will be performed once and recorded in the respective CRF for each study. Subjects will sign an ICF before procedures which are specific to this study are performed. Day 1 is the first dose of study drug, which will be used to calculate future visit dates.

**Subjects who did not participate in Study AXS-05-TRD-201**

Informed consent will be obtained prior to conducting any study-related procedures. Procedures related to eligibility [REDACTED] should be conducted first to confirm eligibility. Subjects may be enrolled once eligibility is confirmed. In select cases, the Day 1 assessments may be conducted across more than one day, with the official Day 1 study day. Day 1 is the first dose of study drug, which will be used to calculate future visit dates.

The following procedures will be performed at Visit 1:

- Obtain written informed consent.
- Review inclusion/exclusion criteria.
- Confirm demographics, medical history, and concomitant medications
- Perform a complete physical examination (excluding breast and genitourinary examination) with review of body systems.
- Conduct 12-Lead ECG after subject has been in the supine position for at least 2 minutes.
- Collect blood sample for serum chemistry analysis.
- Record vital signs (seated blood pressure, pulse, respiratory rate, and oral body temperature) after the subject has been in a seated position for at least 5 minutes and measure height and weight.
- Perform onsite urine pregnancy test for all female subjects of childbearing potential.
- Conduct the following scales:
  - MADRS
  - HAM-A
  - CGI-S
  - CPFQ
  - Q-LES-Q
  - SDS
  - C-SSRS
- Dispense study drug. The first dose should be taken in clinic. Subject should be instructed to take one dose each morning for the next 2 days. On the 4th day of dosing, the subject should begin twice daily dosing.

**9.1.2. Visit 2 (Week 1) and Visit 3 (Week 2) (+/- 2 days)**

The following procedures will be performed at Visits 2 and 3:

- Record vital signs (blood pressure, heart rate, respiratory rate, and oral body temperature) after the subject has been in a seated position for at least 5 minutes.
- Measure weight.
- Conduct the following scales:
  - MADRS
  - HAM-A
  - CGI-S

- CGI-I
- CPFQ
- Q-LES-Q
- SDS
- C-SSRS
- Dispense and/or re-dispense study medication.
- Perform drug accountability.
- Record AEs and concomitant medications.

#### **9.1.3. Visit 4 (Week 4) (+/- 3 days)**

The following procedures will be performed at Visit 4:

- Record vital signs (blood pressure, heart rate, respiratory rate, and oral body temperature) after the subject has been in a seated position for at least 5 minutes.
- Measure weight.
- Perform onsite urine pregnancy test for all female subjects of childbearing potential.
- Conduct the following scales:
  - MADRS
  - HAM-A
  - CGI-S
  - CGI-I
  - CPFQ
  - Q-LES-Q
  - SDS
  - C-SSRS
- Dispense and/or re-dispense study medication.
- Perform drug accountability.
- Record AEs and concomitant medications.

#### **9.1.4. Visit 5 (Week 6) (+/- 3 days)**

The following procedures will be performed at Visit 5:

- Record vital signs (blood pressure, heart rate, respiratory rate, and oral body temperature) after the subject has been in a seated position for at least 5 minutes.
- Measure weight.
- Conduct the following scales:
  - MADRS [REDACTED]
  - HAM-A [REDACTED]
  - CGI-S [REDACTED]

- CGI-I
- CPFQ
- Q-LES-Q
- SDS
- C-SSRS
- Dispense and/or re-dispense study medication.
- Perform drug accountability.
- Record AEs and concomitant medications.

#### **9.1.5. Visits 6 - 18: Months 2 - 14 (+/- 7 days)**

The following procedures will be performed at these study visits:

- Record vital signs (blood pressure, heart rate, respiratory rate, and oral body temperature) after the subject has been in a seated position for at least 5 minutes.
- Measure weight.
- Perform onsite urine pregnancy test for all female subjects of childbearing potential.
- Dispense and/or re-dispense study medication.
- Record AEs and concomitant medications.
- Perform drug accountability.
- C-SSRS
- **Additionally, at Visit 6, the following will occur:**
  - Conduct the following scales:
    - MADRS
    - HAM-A
    - CGI-S
    - CGI-I
    - CPFQ
    - Q-LES-Q
    - SDS
- **Additionally, at Visits 7, 10, 13, and 16, the following will occur:**
  - Perform a complete physical examination (excluding breast and genitourinary examination) with review of body systems. *Brief physical exams may be performed at other study visits in response to subject reported adverse events.*
  - Conduct a 12-Lead ECG after subject has been in the supine position for at least 2 minutes.
  - Collect blood sample for serum chemistry analysis.
  - Conduct the following scales:
    - MADRS
    - HAM-A
    - CGI-S

- CGI-I
- CPFQ
- Q-LES-Q
- SDS

#### **9.1.6. Visits 19 (Month 15), End of Study / Early Termination (+/- 7 days)**

The following procedures will be performed at Visit 19 or Early Termination Visit:

- Perform a complete physical examination (excluding breast and genitourinary examination) with review of body systems.
- Conduct a 12-Lead ECG after subject has been in the supine position for at least 2 minutes.
- Collect blood sample for serum chemistry analysis.
- Record vital signs (blood pressure, heart rate, respiratory rate, and oral body temperature) after the subject has been in a seated position for at least 5 minutes.
- Measure weight.
- Perform onsite urine pregnancy test for all female subjects of childbearing potential.
- Conduct the following scales:
  - MADRS
  - HAM-A
  - CGI-S
  - CGI-I
  - CPFQ
  - Q-LES-Q
  - SDS
  - C-SSRS
- Perform drug accountability.
- Record AEs and concomitant medications.

#### **9.1.7. Unscheduled Visits**

Unscheduled visits may occur as needed during the study. Examples of reasons for unscheduled visit may include dispensing additional study medication or for safety assessments.

### **9.2. Study Duration**

The study will last up to approximately 15 months for an individual subject.

### **9.3. Assessments**

#### **9.3.1. Efficacy**

##### **9.3.1.1. Montgomery-Åsberg Depression Rating Scale (MADRS)**

The MADRS [1] is a clinician-rated scale. The MADRS is used to assess depressive symptomatology during the previous week. Subjects are rated on 10 items to assess feelings of sadness, lassitude, pessimism, inner tension, suicidality, reduced sleep or appetite, difficulty

concentrating and lack of interest. Each item is scored on a 7-point scale. A score of 0 indicates the absence of symptoms, and a score of 6 indicates symptoms of maximum severity.

### **9.3.1.2. Clinical Global Impression – Improvement (CGI-I)**

The CGI-I scale [2] is a clinician-rated scale that is used to rate total improvement or worsening of mental illness regardless of whether the Investigator considers it to be a result of drug treatment or not. The subject is rated on a scale from 1 to 7, with 1 indicating that the subject is very much improved and 7 indicating that the subject is very much worse. The CGI-I will be administered by the Investigator or a Sub-Investigator with extensive professional training and experience in assessing mental illness.

### **9.3.1.3. Clinical Global Impression – Severity (CGI-S)**

The CGI-S scale [2] is a clinician-rated scale used to rate the severity of the subject's current state of mental illness compared with a subject population with TRD. The subject is rated on a scale from 1 to 7, with 1 indicating a "normal state" and 7 indicating "among the most extremely ill subjects." The CGI-S will be administered by the Investigator or a Sub-Investigator with extensive professional training and experience in assessing mental illness.

### **9.3.1.4. Quality of Life Enjoyment and Satisfaction Questionnaire – Short Form (Q-LES-Q-SF)**

The Q-LES-Q-SF [3] is a self-reported questionnaire designed to measure of the degree of enjoyment and satisfaction experienced by subjects in various areas of daily functioning. It is a 16-item questionnaire, where each item is scored from 0 (very poor) to 5 (very good). The total raw score is the sum of the first 14-items, ranging from 14 to 70. The raw total score is transformed into a percentage maximum possible score using the following formula: (raw total score – minimum score) / (maximum possible raw score – minimum score).

### **9.3.1.5. Sheehan Disability Scale (SDS)**

The SDS [4] is a 3-item patient-facing questionnaire used to evaluate impairments in the domains of work, social life/leisure, and family life/home responsibility. All items are rated on an 11-point continuum (0 = no impairment to 10 = most severe).

### **9.3.1.6. Hamilton Rating Scale for Anxiety (HAM-A)**

The HAM-A [5] is a clinician-administered scale which consists of 14 items, each rated on a five-point scale ranging from 0 (not present) to 4 (very severe). The highest possible score is 56, which represents the most severe form of anxiety; the lowest possible score is 0, which represents an absence of anxiety.

### **9.3.1.7. Massachusetts General Hospital Cognitive and Physical Functioning Questionnaire (CPFQ)**

The CPFQ [6] is a 7-item patient-rated scale used to measure cognitive and executive dysfunction in mood and anxiety disorders and was developed to assess clinically relevant cognitive and physical symptoms that could emerge or persist during long-term treatment for depression. Subjects grade the perceived quality of their physical and cognitive functioning. It is scored from 1-6 with increasing severity that individually evaluates 7 distinct items: motivation/enthusiasm, wakefulness/alertness, energy, focus/attention, recall, ability to find words, and sharpness/mental acuity. The physical dimension of the CPFQ assesses sleepiness and fatigue, and the cognitive dimension assesses apathy, inattention, forgetfulness, word-finding difficulties, and mental slowness.

### **9.3.2. Clinical Pharmacology**

Not applicable for this study.

### **9.3.3. Safety**

Safety assessments will include the evaluation of treatment-emergent adverse events (TEAEs), C-SSRS, clinical laboratory test results, ECGs, vital sign measurements, and physical examination findings.

#### **9.3.3.1. Adverse Events**

The definitions and management of and special considerations for AEs are provided in [Section 10](#).

#### **9.3.3.2. Clinical Laboratory Safety Assessments**

##### **9.3.3.2.1. Clinical Laboratory Tests to be Performed**

Samples for the following laboratory tests will be collected at the time points specified in the Schedule of Assessments.

Serum Chemistry	Albumin, total bilirubin, direct bilirubin, total protein, calcium, alkaline phosphatase, alanine aminotransferase, aspartate aminotransferase, blood urea nitrogen, creatinine, random glucose, sodium, potassium, and chloride.
Urine Pregnancy Test	For females of childbearing potential subjects. A test will be performed on site at each study visit.

##### **9.3.3.2.2. Specimen Handling Requirements**

The transmission of infectious agents may occur through contact with contaminated needles and blood or blood products. Consequently, appropriate blood and body fluid precautions should be employed by all study personnel involved in the collection of blood and handling of specimens in both the clinic and laboratory settings. Refer to current recommendations of the appropriate authorities.

In addition to appropriate handling of subject samples, specific regulations exist about the shipment of biologic/etiology samples. Procedures and regulations for the packaging and shipping of infectious samples are outlined in the study laboratory manual. The investigator or designee is responsible for ensuring that all study samples that are to be transported to another location are appropriately packed and shipped according to the applicable regulations.

##### **9.3.3.2.3. Evaluation of Clinical Laboratory Values**

The normal ranges of values for clinical laboratory assessments in this study will be provided by the responsible laboratory and submitted to Axsome before the start of the study. These will be regarded as the reference ranges on which decisions will be made.

If a clinical laboratory value is out of the reference range, it is not necessarily clinically relevant. The investigator is responsible for determining whether these occurrences are considered as AEs.

All clinical laboratory values that in the investigator's opinion show clinically relevant or pathological changes during or after termination of the treatment must be reported as AEs and followed as described in [Section 10.2.5](#).

All measurements described in this section are recognized standard methods.

### **9.3.3.3. Clinical Examinations**

#### **9.3.3.3.1. Vital Signs**

Vital signs will include seated blood pressure, pulse, respiratory rate, and oral body temperature. Blood pressure will be measured after the subject has been in a sitting position for 5 minutes. Height will be collected at Visit 1 and weight will be collected at all study visits.

#### **9.3.3.3.2. Physical Examination**

A complete physical examination (excluding breast and genitourinary examination) will be performed at the time points outlined in the Schedule of Assessments.

#### **9.3.3.3.3. Electrocardiogram (ECG)**

A 12-lead ECG will be conducted after the subject has been resting (supine) for at least 2 minutes. At a minimum, the following parameters should be collected; PR interval, QRS duration, and QTcF.

The date and time of last dose prior to each ECG will be recorded.

If the subject reports cardiac related adverse events, they should return for unscheduled visits and an ECG should be conducted.

#### **9.3.3.3.4. Columbia Suicide Severity Rating Scale (C-SSRS)**

The C-SSRS [7] is a clinician-rated instrument that reports the severity of both suicidal ideation and behavior. Suicidal ideation is classified on a 5-item scale: 1 (wish to be dead), 2 (nonspecific active suicidal thoughts), 3 (active suicidal ideation with any methods [not plan] without intent to act), 4 (active suicidal ideation with some intent to act, without specific plan), and 5 (active suicidal ideation with specific plan and intent). The C-SSRS also captures information about the intensity of ideation, specifically the frequency, duration, controllability, deterrents, and reasons for the most severe types of ideation. Suicidal behavior is classified on a 5-item scale: 0 (no suicidal behavior), 1 (preparatory acts or behavior), 2 (aborted attempt), 3 (interrupted attempt), and 4 (actual attempt). More than 1 classification can be selected provided they represent separate episodes. For actual attempts only, the actual or potential lethality is classified for the initial, most lethal, and most recent attempts.

At all visits the C-SSRS will be completed for ideation and behavior with a recall period since the last visit.

The C-SSRS will be administered by the Investigator or designee.

## **10. ADVERSE EVENTS**

### **10.1. Definitions**

#### **10.1.1. Adverse Events**

An AE is defined as any untoward medical occurrence in a patient or clinical investigation subject administered a pharmaceutical product that does not necessarily have a causal relationship with the product. An AE can therefore be any unfavorable and unintended sign (including a new, clinically important abnormal laboratory finding), symptom, or disease, temporally associated with the product, whether or not related to the product.

Pre-existing diseases or conditions will not be considered AEs unless there is an increase in the frequency or severity, or a change in the quality, of the disease or condition. (Worsening of a pre-existing condition is considered an AE.)

### 10.1.2. Adverse Drug Reaction

All noxious and unintended responses to a study drug related to any dose should be considered adverse drug reactions (ADRs).

The phrase “related to study drug” means that a causal relationship between a study drug and an AE is at least a reasonable possibility, i.e., the relationship cannot be ruled out. All AEs judged by either the reporting investigator or the sponsor as having a reasonable causal relationship to a study drug qualify as ADRs.

All AEs for which the judgment of relationship to the study drug is “possible” or higher will be considered ADRs. If a relationship to the study drug is not given, then the AE must be treated as if the relationship to the study drug were “possible.”

### 10.1.3. Unexpected Adverse Event/Adverse Drug Reaction

An expected AE or ADR is an event for which the nature or severity is consistent with the known AE profile of the product. For a study drug, the known information is contained in the IB. For a marketed product, the known information is contained in the current package insert for the product.

An unexpected adverse event (UAE) or unexpected adverse drug reaction (UADR) is an event for which the specificity or severity is not consistent with the current IB. For example, hepatic necrosis would be unexpected (greater severity) if the IB only listed elevated hepatic enzymes or hepatitis. Likewise, cerebral thromboembolism and cerebral vasculitis would be unexpected (greater specificity) if the IB only listed cerebral vascular accidents.

Furthermore, reports that add significant information on specificity or severity of a known, already documented adverse reaction constitute unexpected events. Examples would be a) acute renal failure as an expected adverse reaction with a subsequent new occurrence of interstitial nephritis (interstitial nephritis would be unexpected) and b) hepatitis with a first occurrence of fulminant hepatitis (fulminant hepatitis would be unexpected).

### 10.1.4. Serious Adverse Events/Drug Reaction

A serious adverse event (SAE) is any untoward medical occurrence that at any dose:

- Results in death.
- Is life-threatening.

*NOTE: The term “life-threatening” in the definition of “serious” refers to an event in which the subject was at risk of death at the time of the event; it does not refer to an event which hypothetically might have caused death if it were more severe.*

- Requires inpatient hospitalization or prolongation of existing hospitalization. *NOTE: Inpatient hospitalization is defined as 24 hours in a hospital or an overnight stay. Anelective hospital admission to treat a condition present before exposure to the study drug, ora hospital admission for a diagnostic evaluation of an AE, does not qualify the condition orevent as an SAE. Further, an overnight stay in the hospital that is only due to transportation,organization, or accommodation problems and without medical background does not need to be considered an SAE.*
- Results in persistent or significant disability/incapacity.
- Is a congenital anomaly.

*NOTE: A congenital anomaly in an infant born to a mother who was exposed to the study drug during pregnancy is an SAE. However, a newly diagnosed pregnancy in a subject who has received a study drug is not considered an SAE unless it is suspected that the study*

*drug(s) interacted with a contraceptive method and led to the pregnancy.*

- Is an important medical event.

*NOTE: Medical and scientific judgment should be exercised in deciding whether it is appropriate to consider other situations serious, such as important medical events that may not be immediately life-threatening or result in death or hospitalization but may jeopardize the subject or may require intervention to prevent 1 of the other outcomes listed in the definition above. Examples of such events are intensive treatment in an emergency room or at home for allergic bronchospasm, blood dyscrasias or convulsions that do not result in hospitalization, or development of drug dependency or drug abuse. The occurrence of malignant tumors is also to be considered serious.*

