#### **10.2.6. Notification of Serious Adverse Events**

The investigator or designee must report all SAEs within 24 hours of first becoming aware of the event by completing the Serious Adverse Event Report Form. [REDACTED]

[REDACTED] At the time of first notification, the investigator or designee should provide the following information, if available:

- Protocol number.
- Reporter (study site and investigator).
- Subject's study number.
- Subject's year of birth.
- Subject's sex.
- Date of last dose of study drug.
- Adverse event term.
- Date of occurrence of the event.
- A brief description of the event, outcome to date, and any actions taken.
- The seriousness criteria(on) that were met.
- Concomitant medication at onset of the event.
- Relevant past history information.
- Relevant laboratory test findings.
- Investigator's opinion of the relationship to the study drug(s). ("Is there a reasonable possibility that the study drug caused the SAE? Yes, or No?").

The investigator must also promptly provide any available supporting information which is requested after review of the initial SAE Report Form.

Any missing or additional relevant information concerning the SAE should be provided in a follow-up SAE Report Form. Ensure that any additional information requested about the event (e.g., hospital reports, autopsy reports) is provided as soon as it is available.

The investigator is required to comply with applicable regulations (including local laws and guidance's) regarding the notification of his or her health authorities, Institutional Review Board (IRB)/Independent Ethics Committee (IEC), principal and coordinating investigators, study investigators, and institutions. The detailed reporting duties and division of responsibilities between Axsome and designated vendors will be provided in a separate document. Each investigator is obligated to learn about the reporting requirements for investigators in his or her country. The study monitor may be able to assist with this.

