10.2. Adverse Events

Each AE and SAE term will be recorded as a verbatim term on the case report forms (CRFs). All AEs and SAEs will be coded by primary system organ class (SOC) and mapped to a preferred term using the MedDRA dictionary Version 22. The investigator will assess AE severity and relationship to the study treatment.

All AEs will be listed. However, only treatment emergent adverse events (TEAEs) will be included in the AE summaries. A TEAE is defined as any AE with an onset date in the interval between the first study treatment dosing date and 7 days after the last study treatment dosing date. In addition, any AEs occurring after the first dose that the investigators deem to be treatment related will also be considered TEAEs and will be included in the AE summaries.

For the purpose of calculating treatment emergence and inclusion in summary tables, incomplete onset dates will be imputed using the method described in [Appendix 1](#).

AEs will be summarized by the number and percentage of subjects in each primary SOC and preferred term. Subjects will be counted only once for each primary SOC and each preferred term. Summary tables of AEs by primary SOC, preferred term and severity will be provided. If a subject has more than one AE coded to the same preferred term, the subject will be counted only once for that preferred term by using the event with the highest severity. Similarly, if a subject has more than one AE within a primary SOC category, the subject will be counted only once in that SOC category by using the event with the highest severity. AEs by primary SOC, preferred term and relationship to study drug will be provided as well. In addition, serious adverse events (SAEs) by primary SOC and preferred term will be provided. Deaths and SAEs will be summarized similarly to AEs. All adverse event tables will also include the total number of events, counting multiple events per Subject.

In the AE summary, preferred terms within each SOC will appear in frequency order.

Frequencies for deaths and hospitalizations will also be summarized by treatment group and overall.

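### The SAE definition exempts every admission for diagnostic work-up of an AE, with no limit to elective or pre-existing conditions, so some new on-treatment admissions can be classed as nonserious

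*Protocol*

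**What the plan says.** Protocol Section 10.1.4 lists as a seriousness criterion that the event "Requires inpatient hospitalization or prolongation of existing hospitalization". The attached note sets the threshold: "Inpatient hospitalization is defined as 24 hours in a hospital or an overnight stay". The same note then gives three exemptions:

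- an elective "hospital admission to treat a condition present before exposure to the study drug";
- a "hospital admission for a diagnostic evaluation of an AE, does not qualify the condition" or event as an SAE;
- an overnight stay due only to transport, organization or "accommodation problems and without medical background does not need to be considered an SAE".

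Section 10.1.4 also keeps the criteria of death, threat to life, disability and congenital anomaly, and a judgment-based criterion for important medical events: "Medical and scientific judgment should be exercised in deciding whether it is appropriate to consider other situations serious".

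Protocol Section 10.2.2.2 sends the investigator back to Section 10.1.4 to judge seriousness. Under Section 10.2.6 the site "must report all SAEs within 24 hours of first becoming aware of the event". SAP Section 6.3 takes its AE definitions from protocol Section 10. SAP Section 10.2 plans an SAE table by system organ class and preferred term, and adds: "Frequencies for deaths and hospitalizations will also be summarized by treatment group and overall". The SAP does not define hospitalization.

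**The concern.** The first and third exemptions remove admissions that say little about the drug: planned care for an old condition, and stays with no medical reason. The second removes admissions for adverse events, which are what this study is meant to detect. Nothing in the clause restricts it by urgency, length of stay or whether the event is new.

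Long-term safety is the primary objective, treatment lasts up to 15 months, no DSMB is convened (Section 11) and no AEs of special interest are defined (Section 10.3.1). Correct classification as serious therefore carries much of the weight for prompt safety review. If a site applies the clause as written, an unplanned overnight admission can be classed as nonserious. The report could then show on-treatment hospitalizations that are not SAEs, with no rule explaining the difference.

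**Working it through.** The plan states no figure on this point, so there is nothing to reproduce. The check is mainly textual.

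**Step 1. Scope of the exemption.** In the sentence that holds the first two exemptions, the word elective and the reference to a condition present before exposure both attach to the admission for treatment. The diagnostic admission is a separate item joined by 'or', and neither limit reaches it. (Run-together words in this note come from reading the PDF and do not affect the sense.)

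**Step 2. A test case.** Take a subject on study drug with a first syncope, kept overnight for observation, not treated, and discharged. The stay meets the overnight threshold. The event is new and the admission is unplanned, so the first exemption does not apply. The stay has a medical reason, so the third does not apply. The second does apply, and the event is not serious under the hospitalization criterion. It can be serious only under another criterion, in practice important medical event. That criterion depends on judgment, and its wording is aimed at events that may not lead to hospitalization, so a site may not think of it for a subject who was admitted.

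**Step 3. What follows from the classification.**

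| Step | If serious | If nonserious |
|---|---|---|
| Site to sponsor | SAE form within 24 hours (Protocol 10.2.6) | eCRF entry, reviewed by the sponsor regularly (10.2.6.3) |
| Sponsor to authorities, if drug-related | Immediately (10.2.6.2) | After study completion (10.2.6.2) |
| SAE table (SAP 10.2) | Included | Absent |
| AE listing and TEAE tables (SAP 10.2) | Included | Included |
| Primary endpoint, TEAE incidence (Protocol 12.1.1) | Counted | Counted |
| Hospitalization summary (SAP 10.2) | Probably included | Unclear, because the term is undefined |

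**Step 4. Size.** Planned enrolment is about 150 (Protocol 12.2). One subject is 1/150 = 0.67%, so each subject whose only SAE is excluded lowers SAE incidence by 0.67 percentage points.

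The number of such subjects depends on two quantities that the documents do not give: h, the share of subjects admitted for an AE, and d, the share of those admissions made for diagnostic evaluation. As an illustration only, assume h of 1% to 5% and d of 10% to 50%. The expected number affected is 150 × h × d, and the chance of at least one is 1 − (1 − hd)^150.

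| h | d | Expected subjects affected | Chance of at least one |
|---|---|---|---|
| 1% | 10% | 0.15 | 14% |
| 2% | 25% | 0.75 | 53% |
| 5% | 50% | 3.75 | 98% |

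For the assumed h and d these are upper bounds, because some of these events would be serious under another criterion. The width of the range shows that the documents cannot settle the number.

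**The case against.** The clause is a stated exception, placed in the note to the criterion that it qualifies. A reader might infer that the protocol contradicts itself. It does not: a rule with an explicit exception is consistent, and the complaint can only be that the exception is too broad for its purpose. That objection stands.

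A reader might also infer that these admissions disappear from the safety data. The documents do not support that. The AE is recorded, listed and tabulated by severity and relationship, the primary endpoint does not depend on seriousness, and the hospitalization summary may show the admission. Section 10.2.3 also gives hospitalization as an example when it asks for seriousness on the eCRF, so a site may be prompted to reconsider.

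Some striking examples are weak. Section 10.1.4 itself names convulsions not leading to hospitalization among important medical events, so a confirmed seizure has another route to SAE status. Pancreatitis treated during the stay is no longer an admission for evaluation alone. Syncope with observation only is the cleaner case, and even there the investigator may judge it an important medical event.

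Nor is the SAE rule the only special reporting route. Pregnancy has its own 24-hour report (Section 10.3.2), and overdose without an AE is reported in writing to the SAE contacts (Section 10.3.3). Neither route covers the test case.

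Finally, the protocol's background reports few SAEs on AXS-05 in earlier trials (three in the TRD trial), and it is tempting to say that one or two reclassified events would change that picture. The SAE definitions used in those trials are not given, so the comparison shows nothing about this clause.

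What remains is the absence of any limit on the exemption, and its effect on reporting speed and the SAE table for events that meet no other criterion.

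**Conclusion.** The concern holds in a limited form. Section 10.1.4 contains an over-broad exception in tension with its own hospitalization criterion. For a new on-treatment AE that leads to a 24-hour or overnight stay for evaluation and meets no other seriousness criterion, following the text as written removes the 24-hour report, moves any report to authorities from immediate to end of study, and leaves the event out of the SAE table. TEAE incidence is unaffected.

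The effect is 0.67 percentage points of SAE incidence per affected subject, at 150 subjects. This assumes that the subject has no other SAE. The number of such subjects cannot be determined from the documents. The conclusion also assumes that sites apply the exemption literally and do not rescue the event as medically important.

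**What to change.** Amend the note in protocol Section 10.1.4 in one of two ways:

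- delete the diagnostic-evaluation exemption; or
- limit it to elective admissions for conditions present before first dose.

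Either way, state that an unplanned admission for a new or worsened AE that meets the existing 24-hour or overnight definition counts under the hospitalization criterion, even if it is for evaluation or observation only. Keep the threshold, so that shorter observation stays are not brought in by accident. Keep the other two exemptions unchanged.

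In SAP Section 10.2, define hospitalization for the frequency summary by the same rule, so that this summary and the SAE table can be reconciled.

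The cost is a formal amendment. Protocol Section 13.6 requires sponsor approval, the investigator's signature and IRB/IEC approval before a site may implement a change, so a memo to sites is not enough. The SAP needs one added sentence before it is finalized. Sites would file a few more SAE forms, and the reported SAE count may be slightly less favourable.
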